1.0 Skin Toxicities	
	
Administer IV (methyl)prednisolone (or equivalent) 0.5-1 mg/kg and convert to oral corticosteroids on response, wean over at least 4 weeks
 
Admit to burn and/or consult wound services with attention to supportive care, including fluid and electrolyte balance, minimizing insensible water losses, and preventing infection
 
Given the immune mechanism of action of these medicines, use of immune suppression is warranted and should be offered
 
For mucous membrane involvement of SJS or TEN, appropriate consulting services should be offered to guide management in preventing sequelae from scarring (e.g., ophthalmology; ear, nose, and throat; urology; gynecology; etc, as appropriate)

G4: Skin erythema and blistering/sloughing covering $\geq 10\%$ to $> 30\%$ BSA with associated signs (e.g., erythema, purpura, epidermal detachment, mucous membrane detachment) and/or systemic symptoms and concerning associated blood work abnormalities (e.g., liver function test elevations in the setting of DRESS/DIHS)	
Permanently discontinue ICPI
 
Admit patient immediately to a burn unit or ICU with consulted dermatology and wound care services
 
Consider further consultations based on management of mucosal surfaces (e.g., ophthalmology; urology; gynecology; ear, nose, and throat surgery; etc). Initiate IV (methyl)prednisolone (or equivalent) 1-2 mg/kg, tapering when toxicity resolves to normal
 
IVIG or cyclosporine may also be considered in severe or corticosteroid-unresponsive cases
 
Consider pain/palliative consultation and/or admission in patients presenting with DRESS manifestations

Additional considerations: The usual prohibition of corticosteroids for SJS is not relevant here, as the underlying mechanism is a T-cell immunodirected toxicity
 
Adequate suppression is necessary with corticosteroids or other agents and may be prolonged in cases of DRESS/DIHS
 
All recommendations are expert consensus based, with benefits outweighing harms, and strength of recommendations are moderate
	

ADL=activities of daily living, AE=Adverse event, BSA= body surface area, CBC=complete blood count, CTCAE=Common Terminology Criteria for Adverse Events, DIHS=drug-induced hypersensitivity syndrome, DRESS=drug reaction with eosinophilia and systemic symptoms, G=grade, ICPI=immune checkpoint inhibitor, ICU=intensive care unit, irAE=immune-related adverse event, IV=intravenous, IVIG=intravenous immunoglobulin, NA=not applicable, SCAR=severe cutaneous adverse reactions, SJS=Stevens-Johnson syndrome, SS-A/B= Sjogren's syndrome A/B, TEN=toxic epidermal necrolysis.

**Table A2 Management of GI irAEs in Patients Treated With ICPis**

2.0 GI Toxicities	
2.1 Colitis	
Definition: A disorder characterized by inflammation of the colon	
Diagnostic work-up	
G2	
Work-up of blood (CBC, comprehensive metabolic panel, TSH, ESR, CRP), stool (culture, Clostridium difficile, parasite, CMV or other viral etiology, ova and parasite) should be performed
 
Consider testing for lactoferrin (for patient stratification to determine who needs more urgent endoscopy) and calprotectin (to follow-up on disease activity)
 
Screening laboratories (HIV, hepatitis A and B, and blood QuantiFERON for TB) to prepare patients to start infliximab should be routinely done in patients at high risk for those infections and appropriately selected patients based on infectious disease expert's evaluation
 
Imaging (e.g., CT scan of abdomen and pelvis and GI endoscopy with biopsy) should be considered as there is evidence showing that the presence of ulceration in the colon can predict a corticosteroid-refractory course, which may require early infliximab
 
Consider repeating endoscopy for patients who do not respond to immunosuppressive agents; repeating endoscopy for disease monitoring can be considered when clinically indicated and when planning to resume therapy

G3-4	
All the work-up listed for G2 (blood, stool, imaging, and scope with biopsy) should be completed immediately
 
Consider repeating endoscopy for patients who do not respond to immunosuppressive agents; repeating endoscopy for disease monitoring should only be considered when clinically indicated and when planning to resume ICPi

Grading (based on CTCAE for diarrhea, as most often used clinically)	Management
All patients	
Counsel all patients to be aware of and inform their health care provider immediately if they experience: Abdominal pain, nausea, cramping, blood or mucus in stool or changes in bowel habits Fever, abdominal distention, obstipation, constipation
 
For G2 or higher, consider permanently discontinuing CTLA-4 agents and may restart PD-1, PD-L1 agents if patient can recover to G1 or less; concurrent immunosuppressant maintenance therapy should be considered only if clinically indicated in individual cases

G1: Increase of fewer than four stools per day over baseline; mild increase in ostomy output compared with baseline	
Continue ICPi; alternatively, ICPi may be held temporarily and resumed if toxicity does not exceed G1
 
Monitor for dehydration and recommend dietary changes Facilitate expedited phone contact with patient/caregiver May obtain gastroenterology consult for prolonged G1 cases

G2: Increase of four to six stools per day over baseline; moderate increase in ostomy output compared with baseline	
Should hold ICPi temporarily until patient's symptoms recover to G1; can consider permanently discontinuing CTLA-4 agents and may restart PD-1, PD-L1 agents if patient can recover to G1 or less
 
Concurrent immunosuppressant maintenance therapy (< 10 mg prednisone equivalent dose) may be offered only if clinically indicated in individual cases

2.0 GI Toxicities	
	
May also include supportive care with medications such as Imodium if infection has been ruled out
 
Should consult with gastroenterology for G2 or higher
 
Administer corticosteroids, unless diarrhea is transient, starting with initial dose of 1 mg/kg/day prednisone or equivalent
 
When symptoms improve to G1 or less, taper corticosteroids over at least 4-6 weeks before resuming treatment, although resuming treatment while on low-dose corticosteroid may also be an option after an evaluation of the risks and benefits
 
EGD/colonoscopy, endoscopy evaluation should be highly recommended for cases grade <math>\geq 2</math> to stratify patients for early treatment with infliximab based on the endoscopic findings and to determine the safety of resuming PD-1, PD-L1 therapy
 
Stool inflammatory markers can be considered (lactoferrin and calprotectin) in cases of G2 or higher to differentiate functional v inflammatory diarrhea, and use calprotectin to monitor treatment response if provider prefers
 
Repeat colonoscopy is optional for cases of G2 or higher for disease activity monitoring to achieve complete remission, especially if there is a plan to resume ICPi

G3: Increase of seven or more stools per day over baseline, incontinence, hospitalization indicated, severe increase in ostomy output compared with baseline, limiting self-care ADL	
Should consider permanently discontinuing CTLA-4 agents and may restart PD-1, PD-L1 agents if patient can recover to G1 or less.
 
Administer corticosteroids (initial dose of 1-2 mg/kg/d prednisone or equivalent)
 
Consider hospitalization or outpatient facility for patients with dehydration or electrolyte imbalance
 
If symptoms persist <math>\geq 3-5</math> days or recur after improvement, consider administering IV corticosteroid or noncorticosteroid (e.g., infliximab)
 
Consider colonoscopy in cases where patients have been on immunosuppression and may be at risk for opportunistic infections as an independent cause for diarrhea (i.e., CMV colitis) and for those who are anti-TNF or corticosteroid refractory

G4: Life-threatening consequences; urgent intervention indicated	
Permanently discontinue treatment
 
Should admit patient when clinically indicated; patients managed as outpatients should be very closely monitored
 
Administer 1-2 mg/kg/d methylprednisolone or equivalent until symptoms improve to G1, and then start taper over 4-6 weeks
 
Consider early infliximab 5-10 mg/kg if symptoms refractory to corticosteroid within 2-3 days
 
Consider lower GI endoscopy if symptoms are refractory despite treatment or there is concern of new infections

Additional considerations	
The use of vedolizumab (not approved in Japan) may be considered in patients refractory to infliximab and/or contraindicated to TNF- $\alpha$ blocker. The decision should be made on an individual basis from gastroenterology and oncology evaluation. This is based on case series showing promising results	

2.0 GI Toxicities	
Patients with hepatitis and irAE colitis are rare, and management should include permanently discontinuing ICPi and offering other immunosuppressant agents that work systemically for both conditions	
Currently, enteritis alone as the cause of diarrhea is uncommon and requires small bowel biopsy as the evaluation tool. It may be managed similar as colitis, including corticosteroid and/or infliximab, etc.	
2.2 Hepatitis	

Definition: A disorder characterized by a viral pathologic process involving the liver parenchyma
 
Diagnostic work-up
 
Monitor patient for abnormal liver blood tests: AST, ALT, and bilirubin prior to each infusion and/or weekly if G1 liver function test elevations. No treatment is recommended for G1 liver function test abnormality
 
For G2 or higher:
 
Work-up for other causes of elevated liver enzymes should be tested, viral hepatitis, alcohol history, iron study, thromboembolic event, liver ultrasound, cross-sectional imaging for potential liver metastasis from primary malignancy. If suspicion for primary autoimmune hepatitis is high, can consider ANAs, antismooth muscle antibodies, antineutrophil cytoplasmic antibodies. If patients with elevated alkaline phosphatase alone, g-glutamyl transferase should be tested. For isolated elevation of transaminases, consider checking CK for other etiologies
	
Grading	Management
All patients	
Counsel all patients to be aware of and inform their health care provider immediately if they experience:
 
Yellowing of skin or whites of the eyes
 
Severe nausea or vomiting
 
Pain on the right side of the abdomen
 
Drowsiness
 
Dark urine (tea colored)
 
Bleeding or bruising more easily than normal
 
Feeling less hungry than usual

G1: Asymptomatic (AST or ALT > ULN to 3.0 x ULN and/or total bilirubin > ULN to 1.5 x ULN)	
Continue ICPi with close monitoring; consider alternate etiologies
 
Monitor laboratories one to two times weekly
 
Manage with supportive care for symptom control

G2: Asymptomatic (AST or ALT > 3.0 to $\leq$ 5 x ULN and/or total bilirubin > 1.5 to $\leq$ 3 x ULN)	
Hold ICPi temporarily and resume if recover to G1 or less on prednisone <math>\leq</math> 10 mg/d
 
For grade 2 hepatic toxicity with symptoms, may administer corticosteroid 0.5-1 mg/kg/d prednisone or equivalent if the abnormal elevation persists with significant clinical symptoms in 3-5 days Increase frequency of monitoring to every 3 days
 
Infliximab might not be the most appropriate treatment option in the situation of immune-mediated hepatitis given the potential risk of idiosyncratic liver failure (Note: No clear evidence shows the liver toxicity from infliximab from other studies)
 
In follow-up, may resume ICPi treatment followed by taper only when symptoms improve to G1 or less and corticosteroid <math>\leq</math> 10 mg/d; taper over at least 1 month
 
Patients should be advised to stop unnecessary medications and any known hepatotoxic drugs

G3: Symptomatic liver dysfunction, fibrosis by biopsy, compensated cirrhosis, reactivation of chronic hepatitis (AST or ALT 5-20 x ULN and/or total bilirubin 3-10 x 3 ULN)	
Permanently discontinue ICPi
 
Immediately start corticosteroid 1-2 mg/kg methylprednisolone or equivalent
 
If corticosteroid refractory or no improvement after 3 days, consider mycophenolate mofetil or azathioprine (if using azathioprine should test for thiopurine methyltransferase deficiency)

2.0 GI Toxicities	
	
Laboratories at daily or every other day; consider inpatient monitoring for patients with AST/ALT > 8 x ULN and/or elevated TB 3 x ULN
 
Increase frequency of monitoring to every 1-2 days
 
Infliximab might not be the most appropriate treatment option in the situation of immune-mediated hepatitis given the potential risk of liver failure (Note: No clear evidence shows that the liver toxicity from infliximab from other studies); alternatives include non-TNF-<math>\alpha</math> agents as systemic immunosuppressants. If no improvement is achieved with corticosteroids or for patients on combination therapy with a novel agent, with standard chemotherapy, or with targeted therapy, refer to hepatologist for further pathologic evaluation of hepatitis
 
Corticosteroid taper can be attempted around 4-6 weeks; re-escalate if needed; optimal duration unclear

G4: Decompensated liver function (e.g., ascites, coagulopathy, encephalopathy, coma; AST or ALT > 20 x ULN and/or total bilirubin > 10 x ULN)	
Permanently discontinue ICPi
 
Administer 2 mg/kg/d methylprednisolone equivalents
 
If corticosteroid refractory or no improvement after 3 days, consider mycophenolate mofetil
 
Monitor laboratories daily; consider inpatient monitoring
 
Avoid the use of infliximab in the situation of immune-mediated hepatitis
 
Hepatology consult if no improvement was achieved with corticosteroid
 
Corticosteroid taper can be attempted around 4- 6 weeks when symptoms improve to G1 or less; re-escalate if needed; optimal duration unclear
 
Consider transfer to tertiary care facility if necessary

All recommendations are expert consensus based, with benefits outweighing harms, and strength of recommendations is moderate.	

ADL=activities of daily living, ALT=alanine aminotransferase, ANA=antinuclear antibody, AST= aspartate aminotransferase, CK=creatine kinase, CMV=cytomegalovirus, CRP=C-reactive protein, CT=computed tomography, CTCAE=Common Terminology Criteria for Adverse Events, CTLA-4=cytotoxic T-cell lymphocyte-4, EGD=esophagogastroduodenoscopy, ESR=erythrocyte sedimentation rate, G=grade; ICPi=immune checkpoint inhibitor, irAE=immune-related adverse event, IV=intravenous, PD-1=programmed death 1, PD-L1=programmed death ligand 1, TB=tuberculosis, TNF=tumor necrosis factor, TSH=thyroid-stimulating hormone, ULN=upper limit of normal.

**Table A3 Management of Lung irAEs in Patients Treated With ICPis**

3.0 Lung Toxicities	
3.1 Pneumonitis	

Definition: Focal or diffuse inflammation of the lung parenchyma (typically identified on CT imaging)  No symptomatic, pathologic, or radiographic features are pathognomonic for pneumonitis  Diagnostic work-up  Should include the following: CXR, CT, pulse oximetry  For G2 or higher, may include the following infectious work-up: nasal swab, sputum culture and sensitivity, blood culture and sensitivity, urine culture and sensitivity
	
Grading	Management
G1: Asymptomatic, confined to one lobe of the lung or < 25% of lung parenchyma, clinical or diagnostic observations only	
Continue ICPi  If clinically indicated, monitor participants weekly or more frequently as needed with history, physical examination and pulse oximetry; may also offer CXR. May offer one repeat CT scan in 3-4 weeks; in patients who have had baseline testing, may offer a repeat spirometry/DLCO in 3-4 weeks  If symptoms appear and/or changes in the physical exam are noted, treat as G2

G2: Symptomatic, involves more than one lobe of the lung or 25%-50% of lung parenchyma, medical intervention indicated, limiting instrumental ADL	
Hold ICPi until resolution to G1 or less  Prednisone 1-2 mg/kg/d and taper by 5-10 mg/wk over 4-6 weeks Consider bronchoscopy with BAL  Consider empirical antibiotics  Monitor every 3 days with history and physical examination and pulse oximetry, consider CXR; no clinical improvement after 48-72 hours of prednisone, treat as G3

G3: Severe symptoms, hospitalization required, involves all lung lobes or 50% of lung parenchyma, limiting self-care ADL, oxygen indicated G4: Life-threatening respiratory compromise, urgent intervention indicated (intubation)	
Permanently discontinue ICPi  Empirical antibiotics; (methyl)prednisolone IV 1- 2 mg/kg/d; no improvement after 48 hours, may add infliximab 5 mg/kg or mycophenolate mofetil IV 1 g twice a day or IVIG for 5 days or cyclophosphamide; taper corticosteroids over 4-6 weeks  Pulmonary and infectious disease consults if necessary  Bronchoscopy with BAL ± transbronchial biopsy  Patients should be hospitalized for further management


Additional considerations  GI and Pneumocystis prophylaxis with PPI and Bactrim may be offered to patients on prolonged corticosteroid use (> 12 weeks), according to institutional guidelines  Consider calcium and vitamin D supplementation with prolonged corticosteroid use  The role of prophylactic fluconazole with prolonged corticosteroid use (> 12 weeks) remains unclear, and physicians should proceed according to institutional guidelines  Bronchoscopy + biopsy; if clinical picture is consistent with pneumonitis, no need for biopsy  All recommendations are expert consensus based, with benefits outweighing harms, and strength of recommendations are moderate.
	

ADL=activities of daily living, BAL=bronchoalveolar lavage, CT=computed tomography, CXR=chest x-ray, DLCO=diffusing capacity of lung for carbon monoxide, G= grade, GI=gastrointestinal, ICPi= immune checkpoint inhibitor, irAE=immune-related adverse event, IV=intravenous, IVIG=intravenous immunoglobulin, PPI=proton pump inhibitor.

**Table A4 Management of Endocrine irAEs in Patients Treated With ICPis**

4.0 Endocrine Toxicity	
Counsel patients to inform their health care provider immediately if they experience any changes in their health since their last visit, especially any of the following:	
Headaches that will not go away or unusual headache patterns Vision changes Rapid heartbeat Increased sweating Extreme tiredness or weakness Muscle aches Weight gain or weight loss Dizziness or fainting Feeling more hungry or thirsty than usual Hair loss Changes in mood or behavior, such as decreased sex drive, irritability, or forgetfulness Feeling cold Constipation Voice gets deeper Urinating more often than usual Nausea or vomiting Abdominal pain	
4.1 Thyroid	
4.1.1 Primary hypothyroidism	

Definition: Elevated TSH, normal or low FT4
 
Diagnostic work-up
 
TSH and FT4 every 4-6 weeks as part of routine clinical monitoring on therapy or for case detection in symptomatic patients
	
Grading	Management
G1: TSH < 10 mIU/L and asymptomatic G2: Moderate symptoms; able to perform ADL; TSH persistently > 10 mIU/L	Should continue ICPi with close follow-up and monitoring of TSH, FT4. May hold ICPi until symptoms resolve to baseline Consider endocrine consultation Prescribe thyroid hormone supplementation in symptomatic patients with any degree of TSH elevation or in asymptomatic patients with TSH levels that persist > 10 mIU/L (measured 4 weeks apart) Monitor TSH every 6-8 weeks while titrating hormone replacement to normal TSH. FT4 can be used in the short term (2 weeks) to ensure adequacy of therapy in those with frank hypothyroidism where the FT4 was initially low Once adequately treated, should monitor thyroid function (at least TSH) every 6 weeks while on active ICPi therapy or as needed for symptoms to ensure appropriate replacement; repeat testing annually or as indicated by symptoms once stable
G3-4: Severe symptoms, medically significant or life-threatening consequences, unable to perform ADL	Hold ICPi until symptoms resolve to baseline with appropriate supplementation Endocrine consultation

4.0 Endocrine Toxicity	
	May admit for IV therapy if signs of myxedema (bradycardia, hypothermia) Thyroid supplementation and reassessment as in G2
Additional considerations For patients without risk factors, full replacement can be estimated with an ideal body weight-based dose of approximately 1.6 µg/kg/d For elderly or fragile patients with multiple comorbidities, consider titrating up from low dose, starting at 25- 50 mg Extreme elevations of TSH can be seen in the recovery phase of thyroiditis and can be watched in asymptomatic patients to determine whether there is recovery to normal within 3-4 weeks Under guidance of endocrinology, consider tapering hormone replacement and retesting in patients with a history of thyroiditis (initial thyrotoxic phase) Adrenal dysfunction, if present, must always be replaced before thyroid hormone therapy is initiated	
4.1.2 Hyperthyroidism	
Definition: Suppressed TSH and high normal or elevated FT4 and/or triiodothyronine Diagnostic work-up Monitor TSH, FT4 every 4-6 weeks from the start of therapy or as needed for case detection in symptomatic patients Consider TSH receptor antibodies if there are clinical features and suspicion of Grave disease (e.g., ophthalmopathy) Close monitoring of thyroid function every 2-3 weeks after diagnosis to catch transition to hypothyroidism in patients with thyroiditis and hyperthyroidism	
Grading	Management
G1: Asymptomatic or mild symptoms	Can continue ICPi with close follow-up and monitoring of TSH, FT4 every 2-3 weeks until it is clear whether there will be persistent hyperthyroidism (see below) or hypothyroidism (see 4.1.1) Consider holding ICPi until symptoms return to baseline Consider endocrine consultation b-Blocker (e.g., atenolol, propranolol) for symptomatic relief Hydration and supportive care Corticosteroids are not usually required to shorten duration For persistent hyperthyroidism (> 6 weeks) or clinical suspicion, work-up for Graves disease (TSI or TRAb) and consider thionamide (methimazole or PTU) Refer to endocrinology for Graves disease
G3-4: Severe symptoms, medically significant or life-threatening consequences, unable to perform ADL	Hold ICPi until symptoms resolve to baseline with appropriate therapy Endocrine consultation b-Blocker (e.g., atenolol, propranolol) for symptomatic relief For severe symptoms or concern for thyroid storm, hospitalize patient and initiate prednisone 1- 2 mg/kg/d or equivalent tapered over 1-2 weeks; consider also use of SSKI or thionamide (methimazole or PTU).

4.0 Endocrine Toxicity	
Additional considerations Thyroiditis is transient and resolves in a couple of weeks to primary hypothyroidism or normal. Hypothyroidism can be treated as above. Graves disease is generally persistent and is due to increased thyroid hormone production that can be treated with antithyroid medical therapy. Physical examination findings of ophthalmopathy or thyroid bruit are diagnostic of Graves and should prompt early endocrine referral.	
4.2 Adrenal – primary adrenal insufficiency	
Definition: Adrenal gland failure leading to low morning cortisol, high morning ACTH, as well as hyponatremia and hyperkalemia with orthostasis and volume depletion due to loss of aldosterone	
Diagnostic work-up for patients in whom adrenal insufficiency is suspected:  Evaluate ACTH (AM), cortisol level (AM) Basic metabolic panel (Na, K, CO 2 , glucose) Consider ACTH stimulation test for indeterminate results  If primary adrenal insufficiency (high ACTH, low cortisol) is found biochemically:  Evaluate for precipitating cause of crisis such as infection Perform an adrenal CT for metastasis/hemorrhage	
Grading	Management
G1: Asymptomatic or mild symptoms	Consider holding ICPI until patient is stabilized on replacement hormone Endocrine consultation Replacement therapy with prednisone (5-10 mg daily) or hydrocortisone (10-20 mg orally every morning, 5-10 mg orally in early afternoon) May require fludrocortisone (0.1 mg/d) for mineralocorticoid replacement in primary adrenal insufficiency Titrate dose up or down as symptoms dictate
G2: Moderate symptoms, able to perform ADL	Consider holding ICPI until patient is stabilized on replacement hormone Endocrine consultation Initiate outpatient treatment at two to three times maintenance (if prednisone, 20 mg daily; if hydrocortisone, 20- 30 mg in the morning, and 10-20 mg in the afternoon) to manage acute symptoms. Taper stress-dose corticosteroids down to maintenance doses over 5-10 days Maintenance therapy as in G1.
G3-4: Severe symptoms, medically significant or life-threatening consequences, unable to perform ADL	Hold ICPI until patient is stabilized on replacement hormone Endocrine consultation See in clinic or, for after hours, make an emergency department referral for normal saline (at least 2 L) and IV stress-dose corticosteroids on presentation (hydrocortisone 100 mg or dexamethasone 4 mg [if the diagnosis is not clear and stimulation testing will be needed]) Taper stress-dose corticosteroids down to maintenance doses over 7-14 days after discharge

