#### **6.9.2 Immune-Related Adverse Events**

In general, the spectrum of irAEs is similar for M7824 compared with other checkpoint inhibitors. Immune-related AEs are considered AESIs. Effective risk management of these toxicities (irAEs) primarily caused due to inhibition of PD-L1 and PD-1 pathways is based on key recommendations ([Champiat 2016](#)). Participant education for on-time reporting of symptoms of potential irAEs and prompt clinical assessment is critical for effective management and quicker resolution of immune-mediated toxicities, thus preventing progression into severe forms of toxicity that otherwise may become life-threatening and difficult to manage or warrant permanent discontinuation from the study.

Immune-related AEs are specific to immunotherapies and vary by organ system.

The following immune-related AEs are important identified risks for M7824:

- Immune-related hepatitis
- Immune-related pneumonitis
- Immune-related colitis

- Immune-related nephritis and renal dysfunction
- Immune-related endocrinopathies (thyroid disorders, adrenal insufficiency, Type 1 diabetes mellitus, pituitary disorders)
- Immune-related rash
- Other immune-related events (myositis, myocarditis, encephalitis)

The following irAEs are important potential risks for M7824:

- Guillain-Barré syndrome
- Uveitis
- Pancreatitis
- Myasthenia gravis/myasthenic syndrome

The Medical Monitor may be involved as needed for follow-up. Details of the diagnostic work-up will be requested by the study team.

For treatment management of irAEs per NCI-CTCAE v5.0 criteria, refer to the ASCO Clinical Practice Guidelines and National Comprehensive Cancer Network (NCCN) irAE management guidelines.

The recommendations for irAE management are guided by the joint ASCO Clinical Practice Guidelines (Brahmer 2018) and NCCN guidelines, listed in [Appendix 6](#).

Treatment of irAEs is mainly dependent upon severity as defined by NCI-CTCAE v5.0. In general, management by NCI-CTCAE v5.0 grading, as per ASCO, is listed below:

- Grade 1: study intervention should be continued with close monitoring, with the exception of some neurologic, hematologic, and cardiac toxicities.
- Grade 2: study intervention may be suspended for most Grade 2 toxicities, with consideration of resuming when symptoms revert to Grade 1 or less. Corticosteroids may be administered (initial dose of 0.5 to 1 mg/kg/day of prednisone or equivalent).

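### Protocol Appendix 6, Table A4 (4.1.1): as printed, the 'low' thyroid hormone starting dose of 25-50 mg conflicts with the full replacement dose of about 1.6 µg/kg/d in the adjacent sentence

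*Protocol*

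**What the plan says.** Table A4 in Appendix 6 covers endocrine immune-related events. Under primary hypothyroidism (4.1.1) the management rows tell sites: "Prescribe thyroid hormone supplementation in symptomatic patients with any degree of TSH elevation". Patients without symptoms are included when TSH stays above 10 mIU/L.

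The additional considerations to that section then give two doses, one after the other:

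- For patients without risk factors: "full replacement can be estimated with an ideal body weight-based dose of approximately 1.6 µg/kg/d".
- For the more vulnerable group: "For elderly or fragile patients with multiple comorbidities, consider titrating up from low dose, starting at 25- 50 mg".

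The second sentence names no dosing interval. No footnote, and no other place in the Protocol or SAP, explains or corrects its unit.

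This is current operative text, not amendment history. Protocol sections 6.6.1 and 6.9.2 send investigators to Appendix 6 for managing immune-related events. Section 6.9.2 lists thyroid disorders among the important identified risks, and the Schedule of Activities includes free T4 and TSH testing, every 6 weeks in the later treatment phase.

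The introduction to Appendix 6 gives its source as the ASCO and NCCN guidance and says that FDA-requested departures appear in bold, underlined type.

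**The concern.** The two sentences concern the same hormone and the same condition. The second is the cautious alternative to the first: start low and work up. As printed, the cautious dose is far above the full one, and it is meant for the participants least able to tolerate an excess.

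A prescriber who took the second sentence at face value would face a unit-scale dosing error. The stake is participant safety in guidance that the protocol tells sites to use. It is not the validity of any planned analysis.

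**Working it through.** The plan states no calculation here that could be reproduced. The check is a unit conversion and a ratio.

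**Inputs**
- Full replacement: 1.6 µg per kg of ideal body weight per day (Table A4, 4.1.1).
- Printed 'low' starting dose: 25-50 mg, no interval given (same place).
- Ideal body weight: not given in the documents. Assumed 50-90 kg, with 40-120 kg as a wider check.
- The printed 25-50 mg is assumed to be a daily dose.

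**Formulas**
- Full dose (µg/d) = 1.6 × ideal body weight (kg).
- Ratio = printed dose (mg) × 1,000 / full dose (µg/d).

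25 mg = 25,000 µg and 50 mg = 50,000 µg.

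| Ideal body weight (assumed) | Full dose | 25 mg ÷ full dose | 50 mg ÷ full dose |
|---|---|---|---|
| 40 kg | 64 µg/d | 391 | 781 |
| 50 kg | 80 µg/d | 313 | 625 |
| 70 kg | 112 µg/d | 223 | 446 |
| 90 kg | 144 µg/d | 174 | 347 |
| 120 kg | 192 µg/d | 130 | 260 |

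Over 50-90 kg the ratio runs from 25,000 / 144 = 174 to 50,000 / 80 = 625. Over 40-120 kg it runs from about 130 to about 780.

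**Does either assumption drive the result?**
- Weight: 25 mg equals 1.6 µg/kg/d only at 25,000 / 1.6 = 15,625 kg.
- Interval: at 90 kg, 25 mg equals 25,000 / 144 = 174 days of full replacement. The printed dose would average down to the full dose only if given about once every 174 days. Nothing in the section suggests such a schedule.

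**The case against.** **The fault may lie in the extraction.** The sentence before prints the micro sign correctly, which argues against a general loss of that symbol. It does not settle the matter, because single Greek letters do appear as Latin ones in this appendix: 'b-Blocker' in section 4.1.2 of the same table and 'g-glutamyl' in Table A2, section 2.2. Elsewhere, in Table A7, section 7.1, the beta is rendered properly, so the Latin letters may equally stand on the sponsor's own page. Only the original page can decide. This objection stands as a caveat.

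**The protocol names a source.** A reader might infer that sites have nothing to resolve the conflict with. That is not so: the introduction to Appendix 6 identifies the ASCO/NCCN guidance, and section 6.9.2 directs sites to the current NCCN guideline. The sentence carries no bold or underlining in the extracted text, so nothing there marks it as an intended departure. A named source makes correction easier, but it does not remove the contradiction from the table.

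**Use of the sentence is far from assured.** A reader might infer that participants will be dosed from it. The documents do not support that. It says 'consider', names no product, and applies only to elderly or fragile participants who need replacement, in a trial that requires ECOG PS 0 to 1 at entry. The management rows call for endocrine consultation to be considered at Grades 1-2 and obtained at Grades 3-4, and TSH is monitored during titration. SAP section 9 says the last participant began treatment on 3 January 2020, before Protocol version 5.0 of 22 June 2021, and the documents do not say how many were still on treatment by then. All of this lowers the likelihood of harm. It does not justify leaving the two sentences as they are.

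**Conclusion.** The point holds as an internal contradiction in current safety guidance. Read as printed, a dose called low is about 174 to 625 times the dose called full, assuming daily dosing and an ideal body weight of 50-90 kg. The exact multiple depends on those two assumptions; the existence of the conflict does not. It is conditional on the original page reading as the extracted text does.

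Two further inferences go beyond the documents. A reader might conclude that one of the two figures, or one of the two units, is the correct one. The documents show only that they cannot both stand, and this review does not choose between them. A reader might also take this as a flaw in the trial's design. The primary endpoint, error rate, sample size and planned analyses do not depend on it.

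**What to change.** 1. Look at the original page of Table A4, section 4.1.1. If the units there are consistent, the point closes.
2. If it reads as here, the sponsor should reconcile the two sentences with each other and with the ASCO/NCCN source. Both should be in one unit, with the dosing interval stated, so that the terms 'low' and 'full' agree with the figures beside them.
3. Notify sites of the corrected line.

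The cost is a page check, a one-line correction to Appendix 6 and a site notification. Nothing in the design, the sample size or the SAP has to change.
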